#### 4. TARGET STUDY POPULATION SPECIFICS

##### 4.1 *Inclusion Criteria*

1. Male  $\geq$  18 years of age, and being scheduled to undergo TURP or Aquablation® and Botox® procedure.
2. Written informed consent obtained from subject and ability for subject to comply with the requirements of the study.

##### 4.2 *Exclusion Criteria*

1. Non-English Speaking
2. Presence of a condition or abnormality that in the opinion of the Investigator would compromise the safety of the patient or the quality of the data.
3. History of receiving Botox® in the bladder, within the previous 12 months.

##### 4.3 *Data Collection Procedures*

Virginia Mason Urology providers will identify patients for potential study participation.

Informed consent will be obtained for all subjects who wish to participate in this trial. Upon consent, study staff will obtain baseline and demographic data, administer AUA symptom score and the UDI-6. At follow up visits, the AUA symptom score, UDI-6, PGI-I, and VM post-procedure questionnaire will be obtained for participating patients. Additional data points under study will be obtained from the subject's electronic medical record.

#### 5. STATISTICAL CONSIDERATIONS

##### 5.1 *Hypotheses*

- a. There is a high rate of bother from OAB symptoms in men with BPH
- b. Botox® injection at the time of TURP or Aquablation® will improve irritative symptoms as compared to baseline.
- c. Botox® injection at the time of TURP or Aquablation® will not increase procedural morbidity, urinary retention rate, or readmission rate.
- d. Plan for future randomized, single-blind study to better evaluate symptomatic improvement pending the results of the study.

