### 1.2 Secondary Objectives

To identify whether concurrent Botox® and TURP or Aquablation® lead to higher rates of urinary retention, longer hospitalization.

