### 1.3 Primary Endpoint

1 week post-operative visit for: trial of void, to assess for rates of postoperative urinary retention.

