### 1.4 Secondary Endpoints

Four and twelve-week post-op visits when AUA symptom score, VM Post Procedure Questionnaire, PGI-I, and UDI-6 questionnaires will be administered. Post void residual obtained via bladder scan.

Hospitalization readmission rates, urinary retention episodes.

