Demographic data, including comorbidities, urodynamics results, post-void residual, uroflow, operative length, estimated blood loss, length of stay, 30 day readmission rate, and 30 day rate of urinary retention will be collected for each subject via the electronic medical record.

All data will be entered into a secure password-protected clinical research database maintained on a Virginia Mason computer.

The goal is to enroll 20 patients based on an estimation of eligible subjects seen within the Virginia Mason urology outpatient clinic. The rate of enrollment is expected to be 1-2 patients per month.

We will be evaluating the impact of Botox® concurrent with TURP or Aquablation® relative to published rates of overactivity and bother after TURP or Aquablation® alone.

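### Hypothesis c and objective 1.2 compare retention, readmission and hospital stay with surgery alone, but a single group of 20 men, all given Botox, can only estimate them

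*Protocol*

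**What the plan says.** Item c of protocol section 5.1 is the only hypothesis about safety: Botox at the time of surgery "will not increase procedural morbidity, urinary retention rate, or readmission rate". Section 1.2, and the same entry in the synopsis, sets the secondary objective of finding out whether the combined procedures "lead to higher rates of urinary retention, longer hospitalization".

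The relevant outcomes appear in three places:
- Section 1.3 makes the 1-week "trial of void, to assess for rates of postoperative urinary retention" the primary endpoint.
- Section 1.4 lists "Hospitalization readmission rates, urinary retention episodes" among the secondary endpoints.
- Section 3.1 says that "length of stay, 30 day readmission rate, and 30 day rate of urinary retention will be collected for each subject" from the medical record.

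On the design, section 4.1 admits men "being scheduled to undergo TURP or Aquablation® and Botox® procedure", so there is no group without Botox. Section 3.1 describes an observational study and plans to judge the impact of Botox "relative to published rates of overactivity and bother after TURP or Aquablation® alone". On size it says: "The goal is to enroll 20 patients based on an estimation of eligible subjects". Section 5.2 plans descriptive statistics for demographics and questionnaires and leaves room for further analyses. Item d of section 5.1 foresees a later randomized study, but only for symptomatic improvement.

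**The concern.** To increase, to be higher and to be longer are all relative terms. Here the natural comparator is the same surgery without Botox, and the protocol supplies none for these outcomes. It therefore states in advance a safety conclusion that its design cannot deliver.

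This matters because retention is the primary endpoint and item c is the only hypothesis about it. With 20 men, a small number of retention episodes or readmissions is quite possible. Set beside a pre-stated hypothesis of no increase, such a count invites a report that the hypothesis was confirmed. The protocol itself says in section 2.2 that no outcome data exist for this combination, so a reassuring statement from this study could carry more weight than it should.

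**Working it through.** **Is there a comparator?** Three sources are possible.

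1. *Concurrent control.* None. Under section 4.1 every participant is scheduled for both procedures.
2. *The patient's own baseline.* Item b of section 5.1 uses this for irritative symptoms, and section 3.1 collects baseline questionnaires for it. Postoperative retention, readmission and length of stay have no value before surgery, so this route is closed for item c and objective 1.2.
3. *Published rates.* Section 3.1 plans this, but names only overactivity and bother. Retention, readmission, morbidity and length of stay are not included.

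**Is there a sample size calculation to reproduce?** No. The figure of 20 is a feasibility figure. At the stated 1 to 2 patients per month, enrolment takes 20/2 = 10 to 20/1 = 20 months, which fits the study duration of about 2 years. It implies nothing about precision.

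**What can 20 men show about a rate?** The input is n = 20 (section 3.1). For k events, the exact (Clopper-Pearson) two-sided 95% limits solve

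- upper limit U: P(X ≤ k | n = 20, p = U) = 0.025
- lower limit L: P(X ≥ k | n = 20, p = L) = 0.025

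For k = 0 the lower limit is 0, and the upper limit has the closed form U = 1 − 0.025^(1/20) = 1 − 0.8316 = 0.1684.

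| Events in 20 | Observed rate | Exact 95% interval |
|---|---|---|
| 0 | 0% | 0% to 16.8% |
| 1 | 5% | 0.1% to 24.9% |
| 2 | 10% | 1.2% to 31.7% |
| 3 | 15% | 3.2% to 37.9% |
| 4 | 20% | 5.7% to 43.7% |

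So the most favourable result possible, no events at all, is still compatible with a true rate of nearly 17%.

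**Can an excess be seen at all?** The protocol gives no reference rate, so I assume a fixed one of 5%, 10%, 15% or 20%. The smallest count r with P(X ≥ r | 20, reference) ≤ 0.025 is then:

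| Assumed reference | Smallest r | Observed rate at r | Tail probability |
|---|---|---|---|
| 5% | 4 | 20% | 0.016 |
| 10% | 6 | 30% | 0.011 |
| 15% | 7 | 35% | 0.022 |
| 20% | 9 | 45% | 0.010 |

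A large excess over a published rate could therefore stand out. It would still be a comparison with different patients treated elsewhere. The asymmetry matters: a striking excess can be noticed, but a low count cannot establish that there is none.

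No arithmetic is offered for length of stay, because the protocol gives no figures from which to start.

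**The case against.** The strongest reply is that the study claims little. It calls itself observational, plans descriptive statistics and specifies no test of item c. Section 5.1 is loosely written (item d is a plan, not a hypothesis), so item c may be only an informal expectation. This stands as an argument about severity. No planned computation is invalid and no data are lost. It does not make the wording fit the design.

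A second reply is that a single group can be set against a historical rate, and that an analysis plan, not available here, may name one. That is fair, so the absence of a reference rate, margin or interval method from the protocol is not held against it. But an analysis plan cannot add a control group, and the wording at issue sits in the protocol's own objective and hypothesis.

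Three stronger readings are tempting and are not supported.
- A reader might infer that the study can say nothing about an increase. That goes too far: a large excess over a published rate would be informative and should be reportable.
- A reader might want to calculate the power to exclude some margin. The protocol plans no such test and states no margin, so the result would depend wholly on invented inputs.
- A reader might add that procedural morbidity is undefined and that retention has three possible measures (1-week trial of void, episodes, 30-day rate). Such definitions can be completed in an analysis plan, and the point here does not depend on them.

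**Conclusion.** The point holds for retention, readmission, procedural morbidity and length of stay. Item c and objective 1.2 are comparative, and the protocol provides no concurrent, baseline or published comparator for these outcomes. The study can estimate them, but with 20 men even a perfect result leaves an upper 95% limit of 16.8%, and 3 events leave 37.9%. These limits assume only that 20 men are analysed and that outcomes are independent between men; fewer evaluable men would widen them. They need no assumed background rate or margin.

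The severity is modest. The harm would arise in interpretation and reporting, not in a planned analysis. The point does not extend to item b, which names baseline as its comparator, or to the symptom comparison with published rates in section 3.1.

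**What to change.** Reword three places and add a short statement to section 5.2.

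- *Objective 1.2 and the synopsis objective:* to estimate urinary retention, 30-day readmission and length of stay after concurrent Botox and TURP or Aquablation.
- *Section 5.1, item c:* restate as the same estimation aim, without a claim of no increase.
- *Section 5.2:* retention and readmission rates will be reported with exact (Clopper-Pearson) 95% confidence intervals, and length of stay will be summarised. Absence of an increase relative to surgery alone will not be concluded from this study. Any published rate used for comparison will be named in advance for each outcome and treated as descriptive context only. An apparent excess may be reported as a signal for controlled study.

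The cost is a small protocol amendment with IRB review under section 7.1, plus a literature choice if published rates are cited. No extra patients or procedures are needed, because these outcomes are already listed in sections 1.3, 1.4 and 3.1. When the retention measure is written in, the 1-week assessment in section 1.3 should be reconciled with the visit narrative in section 3.1, which describes only the four-week and three-month visits. The drawback is a weaker safety statement, but it is one that the data can support.

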## 5.2 Data Analyses

Descriptive statistics will be performed for demographic and survey data. Additional analyses may be performed as appropriate.

## 6. DATA COLLECTION

### 6.1 Records to be kept

Clinical and demographic data is available through electronic medical records and will be entered directly into the study database. Any paper study documents that are generated, such as the questionnaires, will be securely stored and archived for 10 years following study completion.

### 6.2 Secure Storage of Data

All study data will be entered into a secure password-protected clinical research database maintained on a Virginia Mason computer. No PHI will be transferred outside of Virginia Mason.

### 6.3 Quality Assurance

The Clinical Research Program will assess the risk of this trial and will devise and implement an internal monitoring and/or auditing plan for this trial. This plan will be revised as necessary during the life of the trial based upon a variety of factors, including but not limited to: protocol amendments, staff turnover, enrollment metrics, and compliance issues noted.

## 7. HUMAN SUBJECTS

### 7.1 Institutional Review Board (IRB) Review and Informed Consent

This protocol and informed consent document/study information sheet and any subsequent modifications will be reviewed and approved by the IRB at Benaroya Research Institute at Virginia Mason prior to implementation. Informed consent will be obtained from all subjects prior to study entry following Good Clinical Practice and FDA guidelines.

### 7.2 Potential Risks

The risks associated with the completion of questionnaires are the potential to feel uncomfortable or upset and loss of confidentiality.

### 7.3 Subject Confidentiality

All paper records will be kept in a file cabinet within secure Virginia Mason offices during the trial. The database will be maintained on a Virginia Mason computer located on the secure Virginia Mason maintained network, which requires user login for access. Clinical information will not be released without written permission of the subject, except as necessary for monitoring

by the IRB, or CRP. All paper study records will be securely archived by CRP for 10 years following completion of the study.

#### 7.4 Study Modification/Discontinuation

The study may be modified or discontinued at any time by the IRB or Investigator, as part of their duties to ensure that research subjects are protected.

### 8. PUBLICATION OF RESEARCH FINDINGS

Publication of the results of this trial will be governed by the policies and procedures of the journal for which it is submitted. Any presentation, abstract, or manuscript will be made available for review by the Benaroya Research Institute IRB.

